Appropriate statistical approaches will determine differentially expressed (DE) genes from the bulk RNAseq data and DE proteins between HFpEF and the two comparator groups and within clinical or ML computed HFpEF phenogroups. Bioinformatic analyses will assess biological pathways suggested by the DE genes and proteins and examine any discordant information based on RNA versus protein analysis. To address the “abundant RNA/protein” limitation to whole myocardium sampling wherein the large volume of myocyte RNA/proteins may prevent detection of RNA/protein changes in other cells or the interstitium, spatial transcriptomics and in a subset, spatial proteomics will be performed in the FFPE samples. Given the rapidly evolving technology and potential for new publications relevant to this field, these analytic approaches will be reassessed by the MM-HFpEF Core Laboratory and the MM-HFpEF Tissue Working Group prior to proceeding on the first 100 EMB.

Aim 4. Phase 2 Myocardial Tissue Multiomics: In the second 200 HFpEF subjects undergoing research EMB, sample processing techniques, appropriate controls and biologic analyses will be designed by the MM-HFpEF Core Laboratory and the Heart Share MM-HFpEF Working Group to build on findings in Aim 3, evolution in omics technology and other advances in knowledge. Phase 2 analyses will include but not be limited to, snRNA-seq, targeted metabolomics, myofilament functional assessments, further spatial transcriptomic or proteomic analyses, further HFpEF phenogroup characterization and more in-depth study of specific pathways suggested to mediate HFpEF pathophysiology based on Aim 3 findings.

Aim 5. Venous blood samples (5 ml) will be taken from the superior vena cava at the time of RHC and processed for serum (red top tubes) to undergo proteomics analysis to investigate potential novel peripheral biomarkers of unique HFpEF phenogroups defined by myocardial analyses in Aims 3 and 4.

For Aims 3-5, tissue and serum analyses will be performed at Facilities chosen by the MM-HFpEF Core Laboratory and the Heart Share MM-HFpEF Working Group.

[figure not shown]

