3. STUDY DESIGN

3.1 General Description:

Patients will be consented for research RHC (if not planned for clinical purposes; 4.1 Study Procedures - RHC) and/or research EMB. Within six months of participation, patients will have had a clinically indicated transthoracic echocardiogram, NT-proBNP level, complete blood count, basic metabolic panel and electrocardiogram and/or will have these as research studies as part of this study or the Heart Share Deep Phenotyping Protocol (section 3.4).

Patients will initially be classified as “known HFpEF” or “suspected HFpEF” per criteria below (3.2 Study Population). If the patient has known HFpEF or if the patient meets resting hemodynamic criteria ($_{REST}PCWP \geq 15$ mmHg) for HFpEF, the patient will have confirmed HFpEF and the research EMB will be performed (Figure).

If the patient has suspected HFpEF and does not meet resting hemodynamic criteria for HFpEF, the risk of HFpEF will be assessed (Figure).

If the risk of HFpEF is high as evidenced by a H2FpEF score ≥ 3 or a passive leg raise (PLR) PCWP ≥ 18 mmHg, the patient will undergo research EMB. As clinical studies indicate that these patients have impaired functional capacity and increased risk of future HF,^{67,68} they will be classified as pre-HFpEF unless clinically indicated exercise hemodynamic assessment meets criteria for HFpEF (Figure).

If the patient has low risk of HFpEF based on the H2FpEF score or the $_{PLR}PCWP$, the patient does not qualify for research EMB and is classified as “not HFpEF” unless clinically indicated exercise hemodynamic assessment meets criteria for HFpEF (rare).

The research EMB (4.2 Study Procedures – EMB) will be performed using fluoroscopic or echocardiographic guidance per operator preference. If an EMB is indicated clinically, the three research EMB will be performed after the clinical EMB (usually 3-5 biopsies, per clinician specifications) have been obtained. Before and immediately after the research EMB, transthoracic echocardiographic assessment of tricuspid valve structure and regurgitation and pericardial fluid will be performed and findings recorded, along with blood pressure and heart rate.

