3.2 Study Population

3.2.a: Inclusion criteria: Patients with known or suspected HFpEF will be identified by electronic medical record searches, referrals from clinicians, focused screening in the clinical practice including patients scheduled for RHC to diagnose or assess severity of HFpEF, responses to posting of research opportunities or review of patient lists from previous HFpEF studies.

HFpEF criteria

1. Age ≥ 30 years.
2. Left ventricular ejection fraction $\geq 50\%$ measured by echocardiography, CMR or MUGA (measured within one year + clinical stability)
3. Definition of HFpEF: signs and/or symptoms of HF, NYHA functional class II-IV, and at least one of the following:
 - a. Elevated BNP (≥ 75 pg/ml in sinus rhythm or ≥ 225 pg/ml in atrial fibrillation/flutter) or NTproBNP (≥ 225 pg/ml in sinus rhythm or ≥ 675 in atrial fibrillation/flutter) at baseline. Choice of BNP or NTproBNP is based on availability at each clinical center.
 - b. Prior HF hospitalization (primary reason for the hospitalization is HF with elevated natriuretic peptide levels [using the thresholds listed above], requiring IV diuresis for HF, or pulmonary edema or pulmonary vascular congestion on chest radiography).
 - c. Previously documented elevated pulmonary capillary wedge pressure (PCWP) at rest (≥ 15 mmHg) or during exercise (≥ 25 mmHg for supine exercise or PCWP/cardiac output ratio ≥ 2 mmHg/L/min for upright exercise).
 - d. Elevated H₂FPEF score⁶⁹ (≥ 5) or HFA-PEFF⁷⁰ score (≥ 5).

Suspected HFpEF criteria

1. Age ≥ 30 years.
2. Left ventricular ejection fraction $\geq 50\%$ measured by echocardiography, CMR or MUGA (measured within one year + clinical stability)
3. Signs and/or symptoms of HF, NYHA functional class II-IV and all of the following:
 - a. Does not meet BNP or NT-proBNP criteria for HFpEF (above)
 - b. No prior HF hospitalization meeting HF criteria (above)
 - c. No previous hemodynamic catheterization documentation of HF (as above)

3.2.b: Exclusion criteria:

According to current guidelines,⁷¹ patients deemed at increased risk of right ventricular (RV) septal EMB complications as evidenced by any of the below will be excluded.

1. Inadequate echo or fluoroscopic images.
2. Neck anatomy unfavorable for jugular venous cannulation
3. Therapy with direct oral anticoagulants without cessation for a period (age, renal function, and agent specific) deemed adequate to normalize coagulation according to local clinical guidelines.

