4. Previous or ongoing therapy with warfarin with INR ≥ 1.6 measured day before or of EMB
5. Platelet count $< 50,000/\text{ml}$
6. Active bleeding or coagulation disorder
7. Infection or fever
8. Endocarditis
9. Pregnancy
10. Intracardiac thrombus
11. RV Aneurysm
12. Clinically significant tricuspid, pulmonary or aortic valve stenosis
13. Tricuspid or pulmonary mechanical valve prosthesis
14. Left bundle branch block

A known contrast media hypersensitivity is not a contraindication as contrast is not routinely used but the presence of contrast media hypersensitivity should be noted to preclude use. For patients with an indication for anticoagulation (ie atrial fibrillation), who are treated with warfarin, bridging according to local protocols if deemed advisable by the patient's clinician.

Patients with hemodynamically significant left valve disease, pericardial disease, known hypertrophic cardiomyopathy, severe non-revascularized coronary disease, or known inflammatory (i.e. myocarditis or sarcoidosis) or infiltrative (i.e. amyloidosis) cardiac diseases or known non-group 2 pulmonary hypertension are excluded.

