3.4 Primary Study Data Collected from Review of Clinical Records and Study Procedures

3.4.a: Medical History and Physical Examination: age, sex, history of hypertension, diabetes, hyperlipidemia, coronary disease, atrial fibrillation, pacemaker, myocardial infarction, chronic kidney disease, obesity (BMI ≥ 30), collagen vascular disease, lung disease (obstructive, restrictive), previous thoracic radiation or valve disease and blood pressure, heart rate, height, weight.

3.4.b: Laboratory values: creatinine, blood urea nitrogen, NT-proBNP, Hgb, Hct, platelets, white blood cells, and INR day of or day before procedure (only if on warfarin and holding for EMB).

3.4.c: Electrocardiogram: rate, rhythm (sinus, atrial flutter or AF, ventricular pacing), QRS duration, LBBB pattern (yes/no)

3.4.d: Echocardiogram: Left atrial dimension and/or volume (method), LV end diastolic dimension and/or volume (method), LV septal and posterior wall thickness, LV ejection fraction (value/method), right ventricular size (semiquantitative) and function (semiquantitative), aortic, mitral, tricuspid and pulmonary valve function (stenosis or regurgitation grade)

3.4.e: Resting hemodynamics: HR, systemic blood pressure, RA (a,v,mean), RV (systolic, end-diastolic), PA (systolic, diastolic, mean), PCWP (a,v, mean), cardiac output method (Fick indirect, Fick direct, thermodilution), cardiac output, cardiac index, PVR, PA compliance.

3.4.f: Passive Leg Raise hemodynamics: PCWP (a,v, mean)

3.4.g: Clinically indicated exercise hemodynamics (if performed): Exercise method (arm, bike upright, bike supine, other), peak level (watts, other), and same hemodynamic measures as in 3.4.e (as available).

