4.3 Tissue and Data Processing and Storage

4.3.a: Phase 1: First 100 Biopsies: All samples will be placed in sterile, iced saline on the catheterization laboratory table. Immediately after the last biopsy is obtained, the research biopsies will be given to the MM-HFpEF study staff who will place samples on a sterile dry towel to remove saline. One sample will be placed in formalin and will be subsequently embedded in paraffin (FFPE) at the MM-HFpEF Core Laboratory. The other two samples will be flash frozen in individual containers of liquid nitrogen.

4.3.b: Phase 2: Second 200 Biopsies: Samples will be processed as decided by the MM-HFpEF Core Laboratory and the HFpEF Tissue Working Group as Phase 1 enrollment nears completion.

For both phases, venous blood samples (5 ml) will be taken from the superior vena cava, placed in centrifuge tubes (red top), processed in the bio-accession and processing laboratory (BAP) with serum aliquoted into 0.5 ml samples, frozen and shipped with the biopsy specimens to the MM-HFpEF Core laboratory. The samples will be shipped to the MM-HFpEF Core Laboratory where the formalin fixed samples will be embedded in paraffin and frozen samples will be stored at -80 degrees. Deidentified (MM-HFpEF Study #) corresponding baseline, procedural and post-procedural clinical data will be provided within 90 days to the Heart Share Data Translation Center. Follow up data (HF hospitalization, death, presumed cause of death) will be provided yearly for five years after the biopsy.

The data for this trial will be collected in trial-specific electronic data collection forms from source documents by the research staff during the study visit. The study coordinators will be responsible for transmitting the participant unique non-PHI identifiers using standardized data collection instruments to the Heart Share Data Translation Center at Northwestern University. The research coordinators and investigators will perform manual data entry from source documents.

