4.5 Strategies to mitigate Risk to Participants

To minimize risk, operators will need to have averaged at least 20 to 50 RV EMB per year⁷¹ for at least the preceding four years (exclusive of COVID impact in 2020). Continuous electrocardiographic and pulse oximetry monitoring and intermittent blood pressure (if no arterial line used) will be monitored. Echocardiographic assessment for tricuspid valve structure and regurgitation and for pericardial effusion is assessed during each biopsy and at the end of the procedure. After the research EMB, patients are observed for clinical stability in the catheterization laboratory post procedural area as per local clinical protocols and as deemed necessary by the EMB operator. Repeat echo imaging of tricuspid valve structure and regurgitation and for pericardial effusion is performed immediately after the procedure in the catheterization laboratory. Only RV EMB will be performed (lower risk of stroke and arterial bleeding). Only clinically stable patients without high-risk features (see **3.2.b: Exclusion criteria**) will be included.

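### Exclusion item 5 gives the platelet limit per ml, which is 50 per microlitre; check the unit on the original page and correct it if it prints ml

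*Protocol*

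**What the plan says.** Section 3.2.b of the protocol lists the features that put a patient at increased risk from right ventricular septal biopsy. Item 5 reads "Platelet count $< 50,000/\text{ml". It is the only numeric platelet criterion in the document. Section 4.5 (Strategies to mitigate Risk to Participants) refers back to this list as the means of keeping high-risk patients out.

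The count comes from the blood tests in section 3.1, "complete blood count, basic metabolic panel and electrocardiogram". Section 3.4.b lists it among the laboratory values to be recorded, "Hgb, Hct, platelets, white blood cells, and INR day of or day before procedure". Neither place gives a platelet unit or limit.

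Elsewhere ml is used as follows:

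- Section 2, Aim 5: "Venous blood samples (5 ml) will be taken from the superior vena cava at the time of RHC"
- Section 3.2.a, item 3a: "Elevated BNP (≥ 75 pg/ml in sinus rhythm or ≥ 225 pg/ml in atrial fibrillation/flutter"
- Section 4.3: "serum aliquoted into 0.5 ml samples"

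**The concern.** By the protocol's own usage, item 5 is a count per millilitre. On that scale the limit is so low that the item would not do the screening that sections 3.2.b and 4.5 expect of it. That a limit of 50 per microlitre excludes practically nobody is general knowledge about platelet counts, since the protocol gives no reference range, but it is not in dispute.

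The biopsies are taken for research, section 5.0 (Ethical Considerations) anticipates no direct benefit to participants, and up to 10 sites will apply the list. An eligibility limit for such a procedure should not depend on each site silently correcting the unit. Section 4.3 also has staff enter data by hand from source documents, so an unclear unit could carry over into the recorded platelet value.

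**Working it through.** The limit is a fixed figure in the protocol and is not derived from anything else, so there is no calculation of the plan's own to reproduce. The check is a unit conversion and a search for a correcting statement.

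**Inputs**

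- Limit: below 50,000 per ml (section 3.2.b, item 5, as it appears in the available text).
- Planned enrolment: up to 300 patients (section 3.1).
- Conversions: 1 ml = 1,000 microlitres; 1 L = 1,000 ml.

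**Step 1. The limit as written**

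- 50,000 per ml / 1,000 = 50 per microlitre.
- 50,000 per ml x 1,000 = 50,000,000 per L = 0.05 x 10^9/L.

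**Step 2. The same number per microlitre, for comparison only**

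- 50,000 per microlitre x 1,000 = 50,000,000 per ml = 50 x 10^9/L.
- Ratio of the two readings: 50 / 0.05 = 1,000.

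**Step 3. Where the readings lead to different decisions**

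- Below 50 per microlitre, both exclude.
- At 50,000 per microlitre or above, neither excludes.
- From 50 to below 50,000 per microlitre, the per-microlitre reading excludes and the per-ml reading does not.

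**Step 4. How many patients that could be**

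The protocol does not say what share of candidates lies in that band. The shares below are assumptions, and the counts apply only if every site used the literal reading.

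| Assumed share in the band | Share x 300 |
|---|---|
| 0.1% | 0.3 |
| 0.5% | 1.5 |
| 1% | 3 |

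The counts would be lower once item 6 of the same list, "Active bleeding or coagulation disorder", removes some of these patients.

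**Step 5. Does anything in the protocol correct the unit?**

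No. Sections 3.1 and 3.4.b mention the count without a unit. The uses of ml in Aim 5, section 3.2.a and section 4.3 all mean millilitre, so they support the literal reading of item 5.

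**The case against.** The strongest objection is that the slip may not be in the protocol at all. The whole point turns on one letter. A micro sign can be read from a PDF as a plain m, and that would give exactly this string. The string also carries mark-up added in reading. No micro sign appears anywhere in the text, so there is no way to test whether one would have survived. The plain-text uses of ml elsewhere show what ml normally means, but not that this string was read correctly.

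This objection stands in part, and it is why the finding is conditional. It does not dispose of the point: other symbols, such as the greater-or-equal and approximately signs and the superscripts, did come through, so a reading error is possible but not shown to be likely. Anyone with the original page can settle it.

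The second objection is that nobody would apply the literal limit. Sites would probably recognise it as implausible and use their customary laboratory units. The exclusions for direct oral anticoagulants, INR, and bleeding or coagulation disorders (items 3, 4 and 6) still apply, and section 4.5 adds that "operators will need to have averaged at least 20 to 50 RV EMB per year". This is fair. Nothing in the text shows that an ineligible patient would be enrolled, and the objection limits the weight of the point.

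Two smaller objections also have some force. Section 3.4.b gives no units for its other laboratory values either, so the missing platelet unit there is not in itself a fault. The patient counts in step 4 rest on assumed shares and show only the order of size. They are not evidence of harm.

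**Conclusion.** The concern holds as a minor, conditional finding, with medium confidence. In the available text, the only numeric platelet criterion is stated in a unit that makes it 50 per microlitre, 1,000 times lower than the same number per microlitre, and nothing else in the protocol corrects it. If the original page prints ml, an eligibility limit for a research biopsy is wrong as written. If it prints a micro sign, there is no error.

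The likely consequence is small: under the assumed shares and literal use at every site, between 0.3 and 3 of 300 patients. The aims, sample size and analysis are not affected.

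**What to change.** The sponsor should look at item 5 of section 3.2.b on the original page. If it prints ml, correct the unit to the one intended, and show the same unit on the platelets field (section 3.4.b) in the electronic data collection forms described in section 4.3. If it prints a micro sign, leave the item as it is. Which limit is intended is for the sponsor to state; none is proposed here.

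The cost is one check of the page and, if needed, a one-term correction and a unit label on the form.

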3.3 Duration of participation

For patients undergoing research RHC and EMB, the duration of the procedure consumes 4-8 hours (registration, check in, pre-procedural preparation, procedure (30-90 minutes), post-procedure monitoring and dismissal). For patients undergoing clinically indicated RHC without clinically indicated EMB, the portion of the study that involves research is expected to add an additional 5 to 15 minutes to the RHC procedure (for the three EMB). Pre-EMB echocardiography will be performed during access and the EMB procedure itself, so will not add significantly to procedural time. Post-EMB images will be obtained in the interval between EMB and any other RHC measurements (5-10 min). For patients undergoing clinically indicated RHC with clinically indicated EMB, the portion of the study that involves research is expected to add an additional 5 to 10 minutes to the RHC procedure (for three research EMB).

The study will not require any further participation by patients other than that stated above, but participants will be encouraged to participate in the main HeartShare Deep Phenotyping Protocol to maximize phenotypic characterization. Subsequent annual clinical chart review will be performed for up to five years after enrolling to allow analysis of any relationships between study variables (i.e. histopathology, transcriptomic, proteomic or metabolomic findings) and outcomes. The study will end when the tissue samples are analyzed, within approximately 1- 5 years of EMB procedure.

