After the research EMB and post-EMB imaging, other clinically indicated procedures (i.e. exercise hemodynamics, drug studies for pulmonary vascular function) to further evaluate HFpEF will be performed. Patients may participate in other research protocols as long as the studies do not interfere with the study entry algorithm (figure) and the ability to perform the EMB.

After the research EMB and any other clinically indicated procedures, patients will be observed for clinical stability in the catheterization laboratory post procedural area and then discharged according to routine post-procedural practice at the participating site. At discharge and at 30 days post procedure, the clinical record will be reviewed, and a case report form completed documenting any procedural related adverse events due to research RHC or EMB.

Up to 300 patients will be enrolled over a five-year period at up to 10 sites participating in the MM-HFpEF study.

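### Does the study-end sentence in section 3.3 cut short the five-year outcome follow-up promised in section 4.3?

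*Protocol*

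**What the plan says.** Three statements in the Protocol set the timing.

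- Section 3.3, on chart review: "Subsequent annual clinical chart review will be performed for up to five years after enrolling to allow analysis of any relationships between study variables". The variables meant are the histology and omics findings, to be related to outcomes.
- Section 3.3, the next and final sentence: "The study will end when the tissue samples are analyzed, within approximately 1- 5 years of EMB procedure".
- Section 4.3, on data transfer: "Follow up data (HF hospitalization, death, presumed cause of death) will be provided yearly for five years after the biopsy".

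Section 3.1 gives the accrual: "Up to 300 patients will be enrolled over a five-year period at up to 10 sites participating in the MM-HFpEF study". The biopsies fall into two phases, the first 100 and the next 200 (sections 2 and 4.3).

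No section says in so many words that chart review continues after tissue analysis is complete, and none says that it stops then.

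**The concern.** The end sentence names tissue analysis as the only event that ends the study and allows this to happen about one year after biopsy. Section 4.3 promises five years without condition. Only the upper end of the 1 to 5 year range satisfies both for every participant.

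Two further points make the text look unsettled. With five years of accrual, the range cannot describe one calendar date for everyone. Also, 3.3 counts up to five years from enrolment, while 4.3 counts five years from the biopsy.

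At stake would be the outcome data. If a site or an ethics board treated completion of the tissue work as closure, hospitalizations and deaths after that date would not be collected, and analyses relating myocardial findings to outcome would have fewer events.

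**Working it through.** **Inputs.** From the Protocol: up to 300 participants, five-year accrual (3.1), end at 1 to 5 years after biopsy (3.3), and five years of yearly outcome data (4.3). Assumed, because the Protocol does not say: uniform accrual and no deaths or losses. The Protocol gives no person-year or event figure to reproduce. The promise in 4.3 amounts to 300 × 5 = 1500 person-years.

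**Can the range be one study-wide date?** If the first biopsy is at year 0 and the last at year 5, a close one year after the last is at year 6, which is six years after the first. So the range cannot hold for every participant under a single date. It fits a statement about how long the work on a given sample or batch takes.

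**Loss if the sentence did end follow-up.** Let u be biopsy time (0 to 5 years) and L the end, in years.

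- A, one close L years after the last biopsy: follow-up = min(5, 5 + L − u). The mean shortfall is (5 − L)²/10 years, so the share lost is (5 − L)²/50.
- B, a close per phase: with 100 of 300 in Phase 1, that phase ends at u = 5/3. Phase 1 follow-up = min(5, 5/3 + L − u); Phase 2 as in A.
- C, a close per participant: follow-up = L, and the share lost is 1 − L/5.

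| L (years) | A: mean follow-up | A: person-years of 1500 | A: lost | B: mean follow-up | B: lost | C: lost |
|---|---|---|---|---|---|---|
| 1 | 3.40 | 1020 | 32% | 2.39 | 52% | 80% |
| 2 | 4.10 | 1230 | 18% | 3.38 | 32% | 60% |
| 3 | 4.60 | 1380 | 8% | 4.21 | 16% | 40% |
| 4 | 4.90 | 1470 | 2% | 4.80 | 4% | 20% |
| 5 | 5.00 | 1500 | 0% | 5.00 | 0% | 0% |

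Check of B at L = 1: the Phase 1 mean is 5/3 + 1 − 5/6 = 1.83, the Phase 2 mean is 6 − 10/3 = 2.67, and the overall mean is (1.83 + 2 × 2.67)/3 = 2.39.

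**What the loss would mean.** If events accrue in proportion to person-years (a further assumption), standard errors grow by about 1/√(share kept). At L = 1 this is 1/√0.68 = 1.21 under A and 1/√0.20 = 2.24 under C. At L = 5 it is 1 under every reading.

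**Do the passages require any of these readings?**

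1. The chart review is stated immediately before the end sentence, with its own duration and purpose, and is not tied to the laboratory work.
2. Section 4.3 repeats a five-year term, again without reference to tissue analysis.
3. Reading C at one year would cancel nearly all of the annual review that the preceding sentence sets up. No section describes a close per phase, as B needs. A counts from the last biopsy, which the sentence does not say.
4. The ceiling in 3.3 is ordinary wording that leaves room for death or loss. The Protocol gives no gap between enrolment and biopsy long enough to matter for a yearly review.

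**The case for a change.** The strongest case for a change is that 3.3 says the study ends, not that the laboratory work ends, and says so directly after describing the chart review. Up to 10 sites must report for years, study end and follow-up length are protocol matters that an analysis plan would not settle, and one added sentence would remove the doubt with no extra patient visits. Data not collected cannot be recovered later.

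Part of this stands. The sentence is loose, it is not reconciled with 4.3, and the arithmetic is right under each reading. What does not stand is the step from loose wording to lost data. A site that applies 3.3 literally must also apply the sentence before it, and stopping early would mean setting aside two explicit follow-up statements in favour of an approximate closing remark. Losses that run from 0% to 80% show how open the wording is; they do not estimate a likely effect.

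Making formal study end wait for the last five-year review would also have a cost. With five-year accrual, it puts closure about 5 + 5 = 10 years after first enrolment.

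**Conclusion.** The end sentence in 3.3 is imprecise, and no change to the plan is called for. The conflict with 4.3 is conditional: it arises only if the tissue work ends before five years and someone then treats that as ending chart review, which neither follow-up statement supports. The gap is one that the sponsor and sites fill sensibly by following those two statements.

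The consequence would also be limited. Outcome association is not among Aims 1 to 5, section 6.2 presents the study as exploratory discovery, and no stated design figure depends on follow-up length. The tissue comparisons and the 30-day safety follow-up are untouched. An early close would be administrative censoring. Under A at one year, for example, mean follow-up would be 4.87 years in Phase 1 and 2.67 in Phase 2, which time-to-event methods handle by censoring at the close. The results would be less precise but still valid, provided that closure is unrelated to participants' prognosis.

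The size of any loss cannot be estimated from the Protocol. It is zero at five years, and every non-zero figure above rests on assumed uniform accrual and an end-date reading that the text does not state.
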